2.0 Purpose

The objectives of the study are:

1. To determine the prevalence of externalized conductors at enrollment in Riata®, Riata® ST Silicone, QuickSite®/QuickFlex® and Durata® leads
2. To determine the prevalence of other visual lead anomalies by each subcategory per Appendix A at enrollment in Riata®, Riata® ST Silicone, QuickSite®/QuickFlex® and Durata® leads
3. To determine the prevalence of electrical dysfunction[§] at enrollment in Riata®, Riata® ST Silicone, QuickSite®/QuickFlex® and Durata® leads
4. To determine the incidence of externalized conductors after enrollment in Riata®, Riata® ST Silicone, QuickSite®/QuickFlex® and Durata® leads
5. To determine the incidence of other visual lead anomalies by each subcategory per Appendix A after enrollment in Riata®, Riata® ST Silicone, QuickSite®/QuickFlex® and Durata® leads
6. To determine the incidence of electrical dysfunction[§] after enrollment in Riata®, Riata® ST Silicone, QuickSite®/QuickFlex® and Durata® leads.
7. To evaluate the 30-day adverse event rate associated with lead revision procedures (include lead extractions or abandonments with or without lead replacement) in Riata®, Riata® ST Silicone, QuickSite®/QuickFlex®, and Durata® families of leads
8. To determine the prevalence of “other insulation anomalies” in “returned leads” for Riata®, Riata® ST Silicone, QuickSite®/QuickFlex®, and Durata® families of leads. “Other insulation anomalies” include any of the following:
 - Internal abrasion short under RV shock coil
 - Internal abrasion short under SVC shock coil
 - Exposed conductors defined as a breach of the outer insulation
 - Breach of the internal silicone lumen tubing, but the conductor cable is contained within the lead body diameter.

[§]”Electrical dysfunction” is determined to be present after adjudication of the following cases of potential electrical failures that led to the lead being either

surgically capped/extracted or electrically abandoned. Potential electrical failures include the following:

- Presence of non-physiologic noise not due to external interference
- Rise in pace/sense (p/s) conductor impedance to $> 2000 \Omega$ or increase of more than 200Ω over previous 6 months or increase of 400Ω over any period of time
- Decrease of more than 200Ω over previous 6 months or to impedance $< 200 \Omega$ from baseline impedance $> 300 \Omega$ or decrease of 400Ω over any period of time

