- It is recommended that the Stored EGM Configuration be programmed to the following in patients with

Current/Promote or newer devices ICDs and CRT-Ds:

- RV Bipolar
- RV Unipolar Tip
- Custom: RV Coil to Can (optional)

*** Note:** If patient is pacer dependent or R-wave is not available then RV signal amplitude is not required.

Upon completion of the enrollment visit, complete the enrollment case report form (CRF) using the EDC system and submit the supportive data listed below to St. Jude Medical. Contact and address information are available on the last page of the CRF worksheet.

Enrollment CRF

Electronic device session records

Cinefluoroscopy (AP, LAO 45° or best possible LAO view, RAO 45° or best possible RAO view)

Earliest Chest X-ray or imaging study with evidence of externalized conductors or other visual lead anomalies, if available

Latest Chest X-ray or imaging study with no evidence of externalized conductors or other visual lead anomalies, if available

All eligible patients will be required to undergo the protocol specified follow-up visits. Patient participation in the study will be terminated once the 36 month visit is completed or after all leads being followed by the study are extracted and/or abandoned and the patient is monitored for 30 days.

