3.4.5 Extended Follow-up (Eligible QuickSite/QuickFlex patients only)

The purpose of extending follow-up for eligible patients with QuickSite/QuickFlex leads is to address challenges with fulfilling the minimum number of leads to enroll for the QuickSite/QuickFlex lead group/subgroups as shown in Table 2.

The extended follow-up will help address this issue since the data from patients with extended follow-up will contribute to 2 separate sub-group cohorts for the primary and secondary outcome measure analyses.

For example, a patient who was enrolled with a QuickSite/QuickFlex lead that was implanted for 5 years at the time of enrollment will contribute to the ≥ 5 to <6 year age of lead subgroup cohort (data from lead 5, 6, 7, and 8 years implanted). After this patient provides consent and completes the additional year of follow-up, this patient will also contribute to the ≥ 6 year age of lead subgroup cohort (data from lead 6, 7, 8, and 9 years implanted) as shown in Table 5 below.

Table 5: Extended Follow-Up Example

QS/QF Subgroup cohort Age of Lead @ Enrollment	Primary and Secondary Outcome Measure Data Analyses Timepoints				Extended Follow-up
	Enrollment /Baseline	12 Mo. Visit	24 Mo. Visit	36 Mo. Visit	
≥ 5 and <6 year	5 yr. lead data	6 yr. lead data	7 yr. lead data	8 yr. lead data	9 yr. lead data
≥ 6 year	6 yr. lead data	7 yr. lead data	8 yr. lead data	9 yr. lead data	

Patients eligible for extended follow-up are those already enrolled with QuickSite/QuickFlex leads that have not previously withdrawn and have a QuickSite/QuickFlex lead that will contribute to a second subgroup cohort with an additional year of follow-up.

In order to maintain an unbiased study design, all eligible patients will be approached to provide consent for extended follow-up. SJM will provide study sites with a list of all eligible patients upon approval of this protocol. After eligible patients have been approached to consent for extended follow-up, complete the Extended Follow-Up Consent CRF using the EDC system.

Eligible patients must provide consent for extended follow-up prior to completing the 42 and 48 month follow-up visits (See Section 14.0). Refer to Table 3 and Section 3.4.2 for the requirements for these additional follow-up visits.

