9.0 Withdrawals

Withdrawal is defined as termination of participation of a patient from a clinical trial. All reasonable efforts should be made to retain the subject in the clinical trial until completion of the clinical trial. Reasons for withdrawal include, but are not limited to the following:

- Patient Lost to Follow-up - must be documented by two documented phone calls and one certified letter
- Death
- Patient had an explanted or abandoned Riata/ Riata ST RV lead and no other lead under investigation is currently implanted
- Patient had an explanted or abandoned Durata RV lead and no other lead under investigation is currently implanted
- Patient had an explanted or abandoned QuickSite/QuickFlex 1056T, 1058T, 1156T, or 1158T lead and no other lead under investigation is currently implanted
- Patient/Family request
- Participation terminated by Physician

Patient Relocation: If a patient moves from the geographic area of the investigator, then SJM will first attempt to place the patient with another St. Jude Medical Cardiac Lead Assessment Study investigator. If it is not possible to place the patient with another St. Jude Medical Cardiac Lead Assessment study investigator, SJM will request that the patient's new physician forward the patient's study information to the investigator.

Complete and submit a copy of the Withdrawal form to St. Jude Medical using the EDC system. Contact and address information is available on the Withdrawal form. **If there is a potential withdrawal in the study, please contact a member of the study team to see if there is anything that can be done to keep the patient in the study.**

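### Electrical dysfunction in QuickSite/QuickFlex: extension leads are credited to the older age subgroup from month 12 but selected on later survival, which biases that subgroup's hazard downward

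*Combined protocol and SAP*

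**What the plan says.** Section 3.4.5 extends follow-up to month 48 for some QuickSite/QuickFlex patients so that their leads can fill a second age subgroup. In its example, a lead 5 years old at enrollment also supplies the subgroup of 6 years or more with "data from lead 6, 7, 8, and 9 years implanted". Table 5 shows these to be the patient's own months 12, 24, 36 and 48, so month 12 is the second baseline.

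Membership is settled after month 12:

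- Eligible patients are those who "have not previously withdrawn and have a QuickSite/QuickFlex lead that will contribute to a second subgroup cohort with an additional year of follow-up".
- On timing, "SJM will provide study sites with a list of all eligible patients upon approval of this protocol". Section 3.1.1 expects that approval 32 months after the original FDA approval.
- On consent, "Eligible patients must provide consent for extended follow-up prior to completing the 42 and 48 month follow-up visits".
- The example adds a stronger condition: "After this patient provides consent and completes the additional year of follow-up, this patient will also contribute to the" older subgroup.

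The outcome itself removes leads. Section 2.0 counts electrical dysfunction only where the failure led to the lead being "surgically capped/extracted or electrically abandoned", and the adjudication committee in 11.3 reviews leads taken out of service. Section 9.0 lists as a withdrawal reason "Patient had an explanted or abandoned QuickSite/QuickFlex 1056T, 1058T, 1156T, or 1158T lead and no other lead under investigation is currently implanted", and 3.4.1 ends participation "after all leads being followed by the study are extracted and/or abandoned and the patient is monitored for 30 days".

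Sections 3.2.1.4 and 3.2.2.3 apply the double contribution by cross-reference to 3.4.5. Neither specifies delayed entry, and neither brings in leads that failed before listing.

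**The concern.** A lead that reached the older age at month 12 and then failed before listing is not eligible. Usually the patient has been withdrawn. If another study lead keeps the patient in the study, the failed lead still cannot supply an additional year. A lead that survived to listing is credited from month 12. The months between month 12 and listing therefore enter the older subgroup's denominator and cannot contribute an event to its numerator.

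The plan's safeguard is to approach every eligible patient. That limits selection among eligible patients, but the bias lies in the definition of eligibility.

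At stake are the QuickSite/QuickFlex subgroups that receive carried-over leads (5 to under 6 years, and 6 years or more) in a primary outcome. These are the subgroups in which a rise of hazard with lead age would show. Imaging outcomes are affected less, because a visual anomaly does not by itself end participation.

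**Working it through.** **Plan's figure.** Section 3.1 gives 3-year left ventricular attrition of 43.6%. It reproduces: 1 − (1 − 0.128)³ = 0.337, and 1 − (1 − 0.337)(1 − 0.15) = 0.436. Table 2 raises this to 46% for the two older subgroups, and 46% is used below.

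**Inputs from the documents**
- Table 2: target of 225 leads in each of the two older QuickSite/QuickFlex subgroups, with a minimum of 115.
- Section 3.1.1: listing at month 32. Monthly enrollments after the original approval are 4, 56, 66, 77, 126, 128, 168, 80, 58, 36, 16 and 77, then 217, 135 and 61 over months 13–18, 19–24 and 25–32 (spread evenly here). The total is 1,305 over all lead groups.

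**Assumptions**
- Hazard h = 2% per year, constant, estimated as events divided by lead-years (the plan gives no estimator).
- Exponential attrition, and consent unrelated to hazard.
- Consent rate 50–100%.
- Share of younger leads already enrolled at revision K: 26–100%. The timeline implies up to 2,110 − 2,025 = 85 later QuickSite/QuickFlex enrollments. If all fell in one subgroup, the share is (225 − 85)/225 = 62%, or (115 − 85)/115 = 26%.

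**Event-free window.** For enrollment in month m, w = max(0, 32 − m − 12). The weighted mean is 10.0 of the 36 credited months, and 87% of enrollees are past month 12 at listing. Ignoring attrition, carried-over leads alone would show 1 − 10.0/36 = 0.72 of the true hazard.

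**Lead-years in the subgroup of 6 years or more**
- Attrition rate a = −ln(0.54)/3 = 0.2054 per year, and k = a + h = 0.2254.
- Direct leads: D = 225 × (1 − e^(−3k))/k = 491 lead-years, or 9.8 events.
- Carried-over leads at full share and consent. A lead listed at month s = 12 + w is selected with probability e^(−ks/12). It brings w/12 event-free years and (1 − e^(−k(48 − s)/12))/k years truly at risk. Summed over the timeline and multiplied by 225, this gives E = 116.5 event-free and P = 259.4 at-risk lead-years.

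With q = share × consent, estimated/true hazard = 1 − qE / [D + q(E + P)]:

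- q = 1 (100%, 100%): 1 − 116.5/866.5 = 0.866
- q = 0.31 (62%, 50%): 1 − 36.1/607.1 = 0.941
- q = 0.13 (26%, 50%): 1 − 15.1/539.5 = 0.972

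Hazards of 1% or 3% per year change these ratios by at most about 0.01.

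**Other readings and accrual patterns**

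| When membership is fixed | Ratio, q = 1 to q = 0.13 |
|---|---|
| Listing, pooled timeline (window 10.0 months) | 0.87–0.97 |
| Listing, accrual from month 7 (7.0 months) | 0.90–0.98 |
| Listing, accrual from month 10 (3.9 months) | 0.94–0.99 |
| Listing, accrual from month 13 (2.4 months) | 0.96–0.99 |
| Consent 6 months after listing, failures before consent left out | 0.81–0.96 |
| Same, accrual from month 13 | 0.90–0.98 |
| Consent at month 36, failures before consent left out | 0.72–0.94 |
| Month 48 must be completed (literal example) | 0.64–0.93 |

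With 115 direct leads in place of 225, the listing ratio falls to 0.81 at q = 1.

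**In events.** Failures between month 12 and listing per 225 younger leads are 225 × h × e^(−k) × mean[(1 − e^(−kw/12))/k] = 2.6 (1.3 at 1% per year, 3.9 at 3%). The true 3-year failure probability is 1 − e^(−0.06) = 5.8%. On the pooled timeline the Kaplan-Meier estimate reads 5.2–5.7%.

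**Scale.** Ten events have exact 95% limits of 0.48 to 1.84 times the estimate.

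**The case against.** The case on the other side accepts that credited time before listing can hold no event. Its points are these.

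- **Net sign.** Consent need not be independent of hazard. Patients with drifting measurements may consent more or less often, which adds a bias of unknown sign. This stands: the immortal-time component is downward for certain, but the net sign is downward only if consent is uninformative.
- **Patients with another study lead.** The eligibility sentence could be read as only an age test, so that a failed left ventricular lead is not excluded. This fails: a lead out of service cannot supply an additional year of follow-up.
- **Front-loading.** On the listing reading with q = 1, the ratio by credited year is about 0.71, 0.95 and 1.00; with q = 0.31 it is 0.87, 0.98 and 1.00. The year that the extension adds is unaffected. This is correct, and it limits the harm to the early part of the older subgroup's curve.
- **Rising hazard.** If hazard is proportional to lead age (entry at 6.5 years assumed), the worst listing ratio moves from 0.866 to about 0.88; with the cube of age, to about 0.91. The bias shrinks but remains.
- **Stacked extremes.** The 0.87 end combines full share, full consent and a timeline pooled over lead groups. QuickSite/QuickFlex enrollment was to finish last, which is compatible with later accrual and ratios nearer 1. This is fair, but the group's dates are not given.
- **Consequence.** The excluded failures still count in the lead's original subgroup, and no threshold or between-subgroup test is planned. Both are true, so the error is confined to the older-subgroup estimates.

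**Conclusion.** The concern holds. Followed as written, the rule places event-free time by construction in the older-subgroup denominators for electrical dysfunction, and nothing in 3.2.1.4 or 3.2.2.3 removes it. The mechanism follows from the text alone; the size does not. On the most defensible reading, membership fixed at listing, the hazard in the subgroup of 6 years or more is understated by roughly 3–13% on the pooled timeline and by about 1–4% if accrual began only at month 13. Later consent or a completion condition would make it larger, but the completion wording appears only in the example, and the text does not say whether a failure in the extension year counts as non-completion. All these figures rest on the assumed hazard, consent rate, enrolled share and uninformative consent. The bias is smaller than sampling error, yet it favors the device in a study done under an FDA 522 order and can be avoided. It should be fixed before analysis.

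**What to change.** State in 3.4.5, 3.2.1.4 and 3.2.2.3, and wherever the cross-reference is repeated, that time at risk in the older subgroup never starts before membership is determined.

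Preferred wording:

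> Every QuickSite/QuickFlex lead that is in service, event-free and of the older age at its 12-month visit enters the older subgroup at that visit (time zero), whether or not the patient later joins or completes the extension. All later events count, including those in a part-completed extension year and those in patients who remain with another study lead. The lead is censored at its last assessment, up to month 36 without the extension or month 48 with it.

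Acceptable and narrower: delayed entry (left truncation) at the date membership is fixed, whether listing or consent, with no completion condition. In simulation both return the ratio to about 1.0 (0.99–1.02).

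With either option:
- clarify that censoring at 3 years runs from the second cohort's baseline;
- count each lead-year once in any group-level rate;
- report carried-over and directly enrolled leads separately against the Table 2 minimums.

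The cost is wording, some reprogramming and a protocol revision by the same route as revision K. No new data are needed, because 3.4.2 already requires all patients to attend visits to month 36. The older-subgroup hazard will look less favorable. With 225 younger leads and 80% consent, carried-over lead-years are about 301 as written (93 of them event-free by construction), 371 under the preferred wording and 208 with delayed entry at listing. Under the preferred wording, leads without the extension supply only months 12–36, so the third year carries less information.

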4.0 Protocol Deviations

Investigators are required to adhere to the investigational plan, signed Investigator's Agreement, applicable federal (national) or state/local, laws and regulations, and any conditions required by the IRB/MEC or applicable regulatory authorities.

A protocol deviation is used to describe situations in which the study protocol was not followed. All deviations from the study protocol must be reported to St. Jude Medical as soon as possible but no later than 10 working days of notification of event. In addition, all deviations must be reported to the reviewing IRB per the IRB's reporting requirements.

5.0 Hospitalization

Hospitalization for any reason other than a system revision must be reported to St. Jude Medical via the Hospitalization Case Report Form using the EDC system within 10 working days of the center becoming aware of the patient's admission to the hospital.

6.0 Adverse Events

Adverse events are any unfavorable clinical event which impacts, or has the potential to impact the health or safety of a patient caused by or associated with a study device or intervention. Adverse events will be classified as complication or observations.

Complications: Adverse events that require invasive intervention (e.g. lead dislodgment requiring repositioning).

Observations: Adverse events that can be managed without invasive intervention (e.g., oversensing or loss of pacing capture, which is remedied by reprogramming of the pulse generator).

HV and CRT lead related adverse events along with other adverse events like cardiac tamponade, hematoma, high DFTs, infection and therapy for non-ventricular rhythm will be collected in the study

If the patients with no evidence of externalized conductors by imaging at enrollment show evidence of externalization later in the study, please submit an adverse event form for lead insulation damage (i.e. externalized conductors).

Should an adverse event occur, an Adverse Event Form must be completed and submitted to St. Jude Medical. Report the adverse event to the IRB/MEC per the IRB/MEC policy. Any explanted devices or leads should be returned to St. Jude Medical for analysis.

7.0 Other Reported Events

Other Reported Events is any other clinical event that is submitted by the investigator which is not caused by or associated with the study device and/or system component(s) and/or defined as an Adverse Event in section 6.0.

8.0 Deaths

All patient deaths that occur during this study must be reported to St. Jude Medical within 10 working days of the center being notified. Notification of death should include a detailed statement of the pertinent events and be signed by the investigator in addition to the appropriate case report forms (Patient Death form, Withdrawal form, and Product Out of Service form). It is the investigator's responsibility to notify the IRB/MEC per the IRB/MEC policy. The CEC will review and classify all patient deaths. Details of death and the following information, if available, should be provided in a letter to St. Jude Medical by the investigator summarizing the patient's course since enrollment in the study:

- Date of death
- Place death occurred (e.g. hospital, nursing home, patients home)
- If death was witnessed
- Identification of the rhythm at the time of death, if known
- Cause of death
- Any other circumstances surrounding the death
- Approximate time interval to death from the initiating event
- Autopsy report (if performed)
- Whether it was device and/or procedure related
- Whether it was related to the study
- Device configuration at the time of death

Provide clinical notes and witness statements. If possible, interrogate the pulse generator. Retrieve and print all episode diagnostics, IEGMs, and programmed parameters. If applicable, the pulse generator should then be programmed OFF.

Every attempt should be made to explant the pulse generator and/or leads intact. Any explanted devices or leads should be returned to St. Jude Medical for analysis promptly. In the event that the device is not explanted, the above procedure must be followed to retrieve the data. The reason the pulse generator and/or lead(s) are not being returned to St. Jude Medical must be stated clearly on the case report form.

9.0 Withdrawals

Withdrawal is defined as termination of participation of a patient from a clinical trial. All reasonable efforts should be made to retain the subject in the clinical trial until completion of the clinical trial. Reasons for withdrawal include, but are not limited to the following:

- Patient Lost to Follow-up - must be documented by two documented phone calls and one certified letter
- Death
- Patient had an explanted or abandoned Riata/ Riata ST RV lead and no other lead under investigation is currently implanted
- Patient had an explanted or abandoned Durata RV lead and no other lead under investigation is currently implanted
- Patient had an explanted or abandoned QuickSite/QuickFlex 1056T, 1058T, 1156T, or 1158T lead and no other lead under investigation is currently implanted
- Patient/Family request
- Participation terminated by Physician

Patient Relocation: If a patient moves from the geographic area of the investigator, then SJM will first attempt to place the patient with another St. Jude Medical Cardiac Lead Assessment Study investigator. If it is not possible to place the patient with another St. Jude Medical Cardiac Lead Assessment study investigator, SJM will request that the patient's new physician forward the patient's study information to the investigator.

Complete and submit a copy of the Withdrawal form to St. Jude Medical using the EDC system. Contact and address information is available on the Withdrawal form. **If there is a potential withdrawal in the study, please contact a member of the study team to see if there is anything that can be done to keep the patient in the study.**

